#### 17.1.1 Feasibility (Aim 1.1)

PROTOCOL TITLE: *The impact of sharing audio recorded clinic visits on self-management in older adults: a multisite trial*

We will determine the optimal strategy to achieve a high retention rate and adherence to the study protocol. We will also assess retention rates (proportion of included patients completing T2 follow up; we will target >70% retention), the Feasibility of Intervention Measure (4 items; we will target an average score of >3), and high fidelity to the study protocol (Borelli et al criteria). Reasons for low-recruitment rates (e.g., eligibility criteria restrictions, participant refusal (and reason why, if available), and losses to follow-up) will be gathered as part of the fidelity checklist. If we fall short of targeted thresholds, we will determine the need for deviations from the existing study protocol. We will also gather data on management resources required to conduct the trial i.e., time required to recruit participants, and field notes on any idiosyncratic issues that arise at each site that will be documented and reported to site PIs.

#### 17.1.2 Acceptability (Aim 1.2)

Assessing the proportion of patients and clinicians who agree to take part in the project and proportion of patients who listen to the recording (we will target >70%). Our primary indicator of acceptability will be the recruitment of 108 participants (n=30 patients and 6 clinicians per site) over our planned data collection period of six months. We will determine the listening rates (we will target >70%): this will include the proportion of patients in the intervention arm that log in to the online system and listen to (and how often) the recording. We will also document the number of patients who share or report sharing the recording and caregivers who access the recording. Finally, participants will complete the Acceptability of Intervention Measure (4 items; target an average score of >3). If we fall short of targeted thresholds, we will determine the need for deviations from the existing study protocol. We will contact participants who do not adhere to the listening regime, outside of the standard follow-up assessments to determine if changes are required to the intervention delivery.

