## 4.0 Study Endpoints\*

### 4.1 Primary endpoint

The primary endpoints of this pilot trial are:

1) Feasibility: We will determine the optimal strategy to achieve a high retention rate and adherence to the study protocol. We will also assess retention rates (proportion of included patients completing T2 follow up; we will target >70%), fidelity to the study protocol (Borrelli et al criteria; we will target >90%) and the Feasibility of Intervention Measure (FIM, 4 items, see Appendix 1. 3-month Follow Up Assessment (T2); we will target an average score of >3).

2) Acceptability: We will determine the acceptability of the AUDIO intervention and study protocol by assessing the proportion of patients and clinicians who agree to take part in the project and proportion of patients who listen to the recording. Our primary indicator of acceptability will be the recruitment of 108 participants (N=30 patients and 6 clinicians per site) over our planned data collection period of six months. We will determine the listening rates (we will target >70%): this will include the proportion of patients in the intervention arm that log in to the online system and listen to (and how often) the recording. We will also document the number of patients who share or report sharing the recording and caregivers who access the recording. Participants will complete the Acceptability of Intervention Measure (AIM, 4 items, see Appendix 1. 3-month Follow Up Assessment (T2); target an average score of >3).

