**Health literacy:** We will use two assessments, the 3-item validated Brief Health Literacy Scale (BHLS) and the 18-item validated Short Assessment of Health Literacy (SAHL-E). Both scales are validated in English and Spanish. Scores on the BHLS range between 3 and 15, with higher scores indicating higher subjective health literacy. Scores on the SAHL-E range from 0 – 18; ≤14 is considered low health literacy

**Disease burden:** The Charlson Comorbidity Index (CCI) using EMR data. Each condition is assigned a score, based on risk of death, which is summed, with higher scores indicating higher disease burden.

PROTOCOL TITLE: *The impact of sharing audio recorded clinic visits on self-management in older adults: a multisite trial*

**Depression:** The eight-item PHQ-8 validated in both English and Spanish. Scores range from 0 – 24; a score  $\geq 10$  indicates major depression, and a score of  $\geq 20$  indicates severe major depression.

**Anxiety:** The seven-item GAD-7 validated in both English and Spanish. Scores of 5, 10, and 15 represent cut points for mild, moderate, and severe anxiety, respectively.

**Diabetes Stigma:** The comprehensive diabetes stigma scale (CSSS-15) is a validated 15-item assessment of diabetes-related stigma. It is composed of four subscales: (1) enacted (0-6), (2) perceived (1-5) and (3) self-stigma(1-5), and (4) concealment (1-5). Subscale scores are means of responses, and an overall score is the sum of all items (11-96).

**Stigma of Chronic Illness.** The Stigma Scale for Chronic Illness (SSCI-8) is validated, eight-item assessment of stigma related to chronic disease. It is scored from 8 (low stigma) to 40 (high stigma), and can be converted on to a standardized T-distribution score with a mean of 50 and standard deviation of 10.

**Audio & AVS Use:** Intervention use by patients will be monitored within the HealthPAL application: we can determine when a 1. patient logs into their account; 2. listens to a recording; and 3. shares the recording. AVS use will be assessed at standard outcomes assessments and one week from scheduled clinic visit during the data collection period: we will determine whether the patient reviewed the AVS and whether they shared it.

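### The >70% listening rate has no time cut-off, so listening that first occurs after staff contact about non-adherence counts toward it, although that contact is not part of the described AUDIO intervention

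*Combined protocol and SAP*

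**What the plan says.** Section 4.1 makes acceptability one of the two primary endpoints and gives the listening rate a target above 70%. Section 17.1.2 repeats the target and defines the rate as the "proportion of patients in the intervention arm that log in to the online system and listen to (and how often) the recording". Neither section gives a time window, a minimum amount of listening, or a rule on listening that follows contact by study staff.

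The same paragraph of 17.1.2 then adds: "We will contact participants who do not adhere to the listening regime, outside of the standard follow-up assessments". The stated purpose is "to determine if changes are required to the intervention delivery". The number and timing of these contacts are not given.

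The listening regime is in section 5.1.1: within 24 hours of the visit, at one week, and within three days before the next visit, supported by email and/or text reminders. Section 5 does not mention staff contact with patients who fall behind on it.

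On measurement, section 6.4.1 (Audio & AVS Use) says of the HealthPAL application that "we can determine when a 1. patient logs into their account; 2. listens to a recording", so listening can be dated.

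**The concern.** The plan acts on patients because their use is low, and then has no rule to separate their later use from use that came before. Asking someone why they have not listened can itself lead them to listen, and it may clear up an access problem along the way. Under the definition as written, either outcome turns a non-listener into a listener.

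What is at stake is the interpretation of a result above 70%. A reader would take it as use achieved by the intervention in section 5: recording, instruction by the research assistant, online access and reminders. If part of the figure came from an extra staff contact, it need not carry over to a later trial or to practice without that contact. Section 17.1.2 also says that a shortfall against a target leads to a review of whether the protocol should change. A rate raised by the contact could remove the occasion for that review.

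**Working it through.** The documents give no sample size, power or error rate for the listening rate, so there is no stated figure to reproduce. The check is how far post-contact listening could move the rate.

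**Inputs from the documents**
- Patients: 3 sites × 30 = 90, in agreement with section 26.
- Allocation: blocks of 2 within clinician with equal numbers per arm (section 6.1), so about 90 / 2 = 45 in AUDIO. The arm size is derived, not stated.
- Target: above 70% (sections 4.1 and 17.1.2).

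**Assumed inputs, not in the documents**
- u, the proportion listening before any staff contact: 50% to 65%.
- c, the share of remaining non-listeners who start after contact: 10% to 50%.

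**Who can change status.** A patient who never listens fails the regime as well as the endpoint, so every endpoint non-listener comes within the contact rule. Patients contacted for missing only one point of the regime are already listeners, and the contact cannot change their status.

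**Count needed.** 0.70 × 45 = 31.5, so 32 patients are needed (32/45 = 71.1%).

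**Conversions needed to reach 32**
- From 25/45: 7 of 20 non-listeners (35%).
- From 27/45 (60%): 5 of 18 (28%).
- From 29/45: 3 of 16 (19%).

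In proportions, the conversion that brings the rate to 70% is (0.70 − u)/(1 − u): 40%, 33%, 25% and 14% at u = 50%, 55%, 60% and 65%.

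**Chance of reaching 32 of 45.** The overall rate is p = u + c(1 − u), and the chance is P(Bin(45, p) ≥ 32). At u = 60%:

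| c | p | Chance of at least 32/45 |
|---|---|---|
| 0 | 0.60 | 0.084 |
| 10% | 0.64 | 0.202 |
| 20% | 0.68 | 0.394 |
| 30% | 0.72 | 0.626 |
| 40% | 0.76 | 0.828 |
| 50% | 0.80 | 0.948 |

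**Other starting rates, with c = 30%**

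| u | Pre-contact listening only | Post-contact listening included |
|---|---|---|
| 50% | 0.003 | 0.244 |
| 55% | 0.020 | 0.422 |
| 60% | 0.084 | 0.626 |
| 65% | 0.244 | 0.807 |

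**Other arm sizes, at u = 60% and c = 30%.** With 36 AUDIO patients (26 needed) the chance goes from 0.090 to 0.572. With 54 (38 needed) it goes from 0.077 to 0.669. The result does not hinge on 45.

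**The case against.** **The contact is an enquiry, not a prompt.** Section 17.1.2 gives its purpose as learning whether delivery needs to change, and no prompting effect is planned. This stands as a description of intent. It does not settle how listening after the enquiry is scored.

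**The plan never says that post-contact listening counts.** That is correct. Counting follows from a definition with no cut-off or exclusion. A reader might infer a deliberate choice to count it, and the documents do not support that.

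**Use is prompted anyway.** A reader might frame the issue as prompted against unprompted listening. That contrast is wrong, because email and text reminders belong to the regime in section 5.1.1. The valid contrast is use under the planned reminders against use after additional staff contact.

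**The trigger is not the endpoint.** A reader might infer that contact follows from failing the endpoint. It follows from missing the stricter regime, so some of those contacted are already listeners. This corrects the description and leaves the arithmetic unchanged, since all never-listeners remain within the contact rule.

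**The stakes are modest.** Section 4.1 says: "Our primary indicator of acceptability will be the recruitment of 108 participants". The 70% figure is a descriptive target with no stop/go rule, and missing it leads only to a review of possible protocol deviations. A reader might infer that the listening rate decides whether AUDIO goes forward; the documents do not say so. The probabilities above show sensitivity and are not the error rates of a formal test.

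**Listening may be high enough for this not to matter.** In the clinic case study in section 3.2.2, 28 of 34 interviewed patients and caregivers (82%) reported listening. At a true rate of 82%, the chance of at least 32/45 is already 0.977. Those were interviewees at clinics that record routinely, so the figure is not directly comparable, but it shows that the problem arises only when pre-contact use is near or below the target.

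**Extra attention before the 3-month PAM-SF.** A reader might infer bias in that comparison. The timing of the contact is not stated, AUDIO patients already receive more staff time by design, and PAM-SF is exploratory and unpowered. The documents do not support a claim of material bias.

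**A pre-contact rule can understate use.** Someone contacted early for missing the 24-hour point might have listened anyway, and a contact that uncovers a login fault may restore use that the intervention should have achieved. This stands, and it is the reason to report two rates.

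**Conclusion.** The concern holds as a gap in the definition of one component of a primary endpoint. Read literally, the listening rate includes patients who first listen after a staff contact that lies outside the intervention in section 5, so a result above 70% could not be attributed to AUDIO as described. The possible effect is large if pre-contact use falls somewhat short of the target: from 60%, five conversions among 18 non-listeners suffice, and the chance of reaching 32 of 45 rises from 8% to between 20% and 95% as conversion runs from 10% to 50%. It is small if pre-contact use is well above 70%.

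These figures rest on an AUDIO arm of about 45, on independent patients, on all non-listeners being contacted, and on assumed listening and conversion rates that the documents do not supply. The concern does not extend to the design, to the recruitment indicator or to PAM-SF.

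**What to change.** 1. Record in REDCap the date of the first staff contact about non-listening for each AUDIO patient. Distinguish it from the question on intervention use that section 6.3 plans one week from any scheduled visit with a participating clinician, which covers both AVS and AUDIO.
2. From the HealthPAL log, report the listening rate before that contact and the overall rate, together with the number of patients contacted. The pre-contact rate is a lower bound for use under the planned reminders. The overall rate is an upper bound, provided that contact does not discourage listening.
3. State in sections 4.1 and 17.1.2, before analysis, that the target is claimed as met by the intervention as described only if the pre-contact rate exceeds 70%. If only the overall rate does, report the target as met with added staff contact.

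The enquiry itself can go ahead as planned. The cost is one date field and a few sentences. HealthPAL already dates listening, and section 6.2 already has contact attempts documented in REDCap, in the context of follow-up. The drawbacks are that the headline rate may be lower and that early contact can make the pre-contact rate conservative, so both rates should be shown.

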#### 17.1.3 Exploratory outcomes (Aim 1.3)

Compared to those receiving UC, patients randomized to also receive audio recordings (AUDIO) of clinic visits will report a greater self-management ability (PAM-SF) at 3 months. Despite their emerging use in primary care, we do not know the impact of audio recordings on patients' self-management. While we are not powered to test this primary hypothesis in the current project, our analytic strategy will enable us to gather crucial preliminary data on the potential effectiveness of AUDIO, preliminary data on mediators and moderators of the AUDIO intervention and refinements to the study protocol that may be required. Our overarching analytic strategy fully exploits the benefits of randomization by making minimalist assumptions and thereby is the most protected from bias due to erroneous modeling assumptions in comparing the AUDIO and UC groups. We later describe more nuanced analyses to allow for problems such as non-compliance, that can enable more statistical power by analyzing the outcome data as a longitudinal series (including control for the baseline value of the outcome) as opposed

PROTOCOL TITLE: *The impact of sharing audio recorded clinic visits on self-management in older adults: a multisite trial*  
to distinct cross-sections, as well as the analyses for the exploratory outcomes.

Because patients' AUDIO status varies within clinician, our statistical analysis of the PAM-SF score at 3 months' accounts for any dependence of the outcomes due to clinician within site effects. Therefore, to maximally benefit from the randomization of patients in physicians and generalize our results to a broader population, we will use a mixed-effect regression model of the form:

$$Y_{ij} = \beta_0 + \beta_1 Dartmouth_j + \beta_2 Vanderbilt_j + \beta_3 Audio_{ij} + \theta_j + \varepsilon_{ij} \quad (1)$$

PROTOCOL TITLE: *The impact of sharing audio recorded clinic visits on self-management in older adults: a multisite trial*

patients assigned to UC who self-report that they recorded their visit and listened to the recording to estimate the quantity, the proportion of takers. Our estimator is based the relation with the just described proportions being substituted on the right-hand-side. This procedure corresponds to substituting the estimated value of  $\hat{\pi}$  for  $\pi$  in (1) as the resulting model can be seen as the second-stage of the two-stage least squares procedure adapted to a mixed-effect outcome model.

**17.1.5 Longitudinal use of recordings:** Another extension of our basic analysis will be to analyze the data from the two follow-up time periods (T1–T2) simultaneously using a longitudinal model. An advantage of this analysis is that it allows the form of the trajectory of the outcome variable over the follow-up time (e.g., is it constant, does it have an initial rise at T1 and then decline, does it grow with time) to be compared to a null model having a constant effect. This analysis provides a more powerful test of the effect of AUDIO than a cross-sectional comparison. In both the cross-sectional analyses of the outcome at a single follow-up time and the longitudinal analyses, the inclusion of the baseline (T0) value of the outcome variable as a covariate and/or making the difference in the outcome between  $T_k$  ( $k = 1, 2$ ) and T0 as the outcome are alternative analyses. Because our study is randomized, it is not necessary to include the outcome variable at T0 as a covariate from a bias standpoint, yet, doing so may improve the precision of our results. The chosen strategy will depend on the extent to which the baseline and follow-up outcomes cluster within patients. If clustering is high (e.g., intra-class correlation coefficient  $> 0.5$ ) we will include the T0 value of the outcome variable as a covariate.

**17.1.6 Overall Predictiveness, Direction of Causality and Mediator Role of PAM-SF:** We first want to explore (i) whether self-management (PAM-SF), affects the exploratory (health) outcomes. We will then perform mediation analyses to decompose the overall effect of AUDIO into its indirect, or mediated, component that acts through PAM-SF and the direct component that affects the health outcomes independently of PAM-SF. With the availability of longitudinal data (1 week, and 3-months) we have the capability of regressing each health outcome on the lagged value of PAM-SF. The analyses in (i) will be performed by adding PAM-SF as a predictor variable and removing the intervention indicator variables from the statistical models used to analyze the health outcomes. Using the product of coefficients method, the effect of the intervention on the mediator is estimated in regression analyses like those described for the analysis of PAM-SF while the effect of the mediator (PAM-SF) on a given health outcome is estimated in a second regression model that also conditions on the AUDIO intervention. The product of the two coefficients corresponding to these effects is the mediation (or indirect) effect of the intervention on the outcome via the mediator while the coefficient for the AUDIO effect is in the latter regression and represents the direct effect of AUDIO. Standard errors will be evaluated using the bootstrap or the PRODCLIN program. A new body

PROTOCOL TITLE: *The impact of sharing audio recorded clinic visits on self-management in older adults: a multisite trial*

of research clarifies sequential ignorability and other assumptions required to obtain causal estimates of mediation effects in randomized studies. In addition to basic exploratory analyses, we will incorporate these new methods of performing mediation analysis into our analyses.

**17.1.7 Missing data analysis:** We will use multiple imputation to cope with missing baseline, interim, and outcome data, protecting our results from bias against all forms of missing data that are classed as missing-at-random. Unlike our primary outcome analyses, multiple imputation will be performed using observations from all time-points simultaneously to allow observed values of outcomes or predictors at one observation time to inform any missing values of study variables at other observation times. Multiple imputation creates multiple completed data sets by drawing random values of missing variables from their predictive distribution given the observed variables for each observation. This approach will address both generalizability and causal validity bias. We will record and report all reasons for dropout and missing data for data-handling checks and to gauge the justifiability of the missing-at-random assumption. We will examine sensitivity of inferences to data missing-not-at-random specified based on information from the reasons for missing data we obtain.

**17.1.8 Moderator analyses:** To explore whether patient health literacy is a modifying factor of the effect of audio on the patient-reported ability to self-manage their care, we add health literacy (denoted HlthLit in the statistical model in (2) and abbreviated as HL) as a main and an interaction variable with AUDIO to the model in (1) to obtain the interaction-effect model:

$$Y_{ij} = \beta_0 + \beta_1 Dartmouth_j + \beta_2 Vanderbilt_j + \beta_4 HlthLit_{ij} + (\beta_3 + \beta_5 HlthLit_{ij}) Audi$$

+ +

where quantifies the extent to which the patient's HL modifies the effect of AUDIO on PAM-SF. A in (2) implies that the effect of AUDIO is lower in patients with high HL and higher in patients with low HL. We will also explore whether the impact of audio recording is greater for individuals at highest risk of poor self-management including those with moderate to severe depression and high disease burden. The variables described for the exploratory analyses will be analyzed using the model in (2) to form an analogous series of secondary and extended analyses for depression, anxiety, stigma and disease burden. Furthermore, we will examine whether 1) the presence of a caregiver or 2) sharing information (recording or AVS) with a caregiver moderates the impact of audio on PAM-SF. We will repeat these analyses to explore interaction effects by sex, race and ethnicity (**Sex as a Biological variable**), reporting interaction size and statistical significance.

**17.1.9 Appropriateness of Study Design:** The use of patient level randomization greatly

**PROTOCOL TITLE:** *The impact of sharing audio recorded clinic visits on self-management in older adults: a multisite trial*

simplifies the statistical analysis plan. Due to randomization, there is no need to include an elaborate array of predictors in the statistical model. Because patients are randomized the impact of clustering by clinician and site on standard errors will be minimal, however we will check to assure comparability of groups at baseline and control as needed. In fact, clinician and site act as blocks as we balance the proportion of patients assigned to AUDIO and UC within each of them to guard against the possibility that by chance any clinicians ended up with all patients being assigned to a given group and to maximally gain from the statistical efficiencies of a balanced design. That is, we essentially have a randomized block design. This allows analyses for site and clinician to be control variables whose inclusion sharpens the precision of our inferences, which are determined primarily off variation within clinician and site

**17.1.10 Appropriateness of Sample Size and Analysis:** Hertzog estimated that a sample of 10 – 40 is adequate to detect feasibility issues and gather preliminary outcome data in a pilot project. With 30 patient participants and 6 clinicians per site (total sample, N=108) we will be able to estimate the operating diagnostics of a future study (e.g., retention rates) and approximate effect sizes with a satisfactory level of precision to 1) determine if a future study is feasible and 2) be able to accurately inform power and sample-size calculations for a future trial. We are not powered to detect significant differences in outcomes.

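### Section 17.1.5 adds baseline PAM-SF to model (1) only if clustering seen after follow-up is high; fixing T0 in advance is a small, nearly free gain in precision

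*Combined protocol and SAP*

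**What the plan says.** For PAM-SF at 3 months, section 17.1.3 states "we will use a mixed-effect regression model of the form" model (1). Its terms are an intercept, two site indicators, AUDIO, a clinician random effect and error; the T0 score is absent. Table 1 shows that PAM-SF is collected at T0, T1 and T2.

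Section 17.1.5 then addresses baseline adjustment, and its scope is wide: "In both the cross-sectional analyses of the outcome at a single follow-up time and the longitudinal analyses". Using T0 as a covariate and/or taking the difference between follow-up "and T0 as the outcome are alternative analyses". The section says that randomization makes T0 unnecessary for avoiding bias, "yet, doing so may improve the precision of our results". The decision is data-dependent: "The chosen strategy will depend on the extent to which the baseline and follow-up outcomes cluster within patients". If clustering is high, with an ICC above 0.5 given as an example, "we will include the T0 value of the outcome variable as a covariate". Nothing is said about the case where clustering is not high, or about which time points enter the ICC.

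Two other places bear on this. Section 17.1.3 describes the longitudinal analysis as controlling for the outcome's baseline value, without a condition. Section 17.1.9 says that baseline comparability will be checked and controlled for as needed.

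**The concern.** The clustering that drives the choice can be known only once follow-up data exist, so the form of the main exploratory comparison is not fixed in advance. The criterion also does not fit its purpose. Section 17.1.5 gives precision as the reason for including T0, but 0.5 is where a change score starts to beat no adjustment. Covariate adjustment starts to pay at a much lower correlation. With moderate correlation, the rule can therefore leave out a useful covariate that has already been collected.

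What is at stake is limited. PAM-SF is exploratory, section 17.1 calls the analysis principally descriptive, and section 17.1.10 says that the trial is not powered for outcome differences. The same section does, however, want the pilot to inform the sample size of a future trial, and a pre-named, slightly more precise estimate serves that aim.

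**Working it through.** **Inputs.** There are 90 patients (30 at each of 3 sites), randomized 1:1 in blocks of 2 within clinician. The retention target in section 4.1 is "proportion of included patients completing T2 follow up; we will target >70"%, so the floor is 0.70 × 90 = 63 patients with T2. For missing data, section 17.1.7 says "multiple imputation will be performed using observations from all time-points simultaneously". The documents give no T0-T2 correlation (rho), SD or effect size for PAM-SF. Rho is therefore assumed over 0.3 to 0.7, and results are in SD units.

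**Break-even points.** Relative to no adjustment:

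- Change score: the variance factor is 2(1 − rho), which equals 1 at rho = 0.5.
- T0 covariate, complete cases: the factor is (1 − rho²)(1 + 1/(n − p − 2)). With n = 63 and p = 4 (intercept, two sites, AUDIO) this is (1 − rho²)(58/57). It equals 1 when rho² = 1/58, that is at rho = 0.13.

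**Rule against always adjusting.** The simulation used 100,000 trials per rho with bivariate normal T0 and T2, site as fixed effects, no treatment or clinician effect, and 63 of 90 T2 values observed completely at random. Missing T2 was imputed from T0, arm and site. The rule was read mechanically: include T0 if the one-way T0-T2 ICC exceeds 0.5, otherwise use model (1). The SD columns give the empirical SD of the AUDIO estimate.

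| rho | P(rule includes T0) | SD, unadjusted | SD, rule | SD, always adjusted | Variance cut, always vs rule |
|---|---|---|---|---|---|
| 0.3 | 0.03 | 0.2505 | 0.2498 | 0.2439 | 5% |
| 0.4 | 0.16 | 0.2482 | 0.2438 | 0.2351 | 7% |
| 0.5 | 0.50 | 0.2444 | 0.2291 | 0.2218 | 6% |
| 0.6 | 0.87 | 0.2391 | 0.2072 | 0.2050 | 2% |
| 0.7 | 0.99 | 0.2333 | 0.1827 | 0.1825 | 0% |

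For example, at rho 0.4 the cut is 1 − (0.2351/0.2438)² = 7%. The 95% half-width goes from 1.96 × 0.2438 = 0.478 SD to 1.96 × 0.2351 = 0.461 SD, about 4% narrower. At rho 0.3 the half-widths are 0.490 and 0.478; at rho 0.5 they are 0.449 and 0.435. A repeat with 20,000 trials per rho gave cuts of about 4%, 7%, 7%, 2% and 0%.

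**If T1 enters the ICC.** Section 17.1.5 does not exclude this. Assume that T1 correlates rho + 0.1 with both T0 and T2. The mean pairwise correlation is then (rho + 2(rho + 0.1))/3 = rho + 0.07, so the threshold is passed more often: in about 32%, 82% and 99% of trials at rho 0.4, 0.5 and 0.6. The cut from always adjusting becomes about 4%, 5%, 2%, 0% and 0% at rho 0.3 to 0.7.

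**When the rule leaves T0 out.** In the trials where a T0-T2 rule excludes T0, adjusting would cut variance by about 4%, 8% and 12% at rho 0.3, 0.4 and 0.5. Averaged over all trials, the cut against the unadjusted imputed model is about 5%, 10% and 18%. The lower set describes the loss when the rule actually excludes T0.

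**Cost and validity.** Against the unadjusted imputed model, adjusting adds 1.2% to the variance if rho is 0 and 0.5% if rho is 0.1. Type I error under the rule (complete cases, 20,000 trials per rho) was 4.8% to 5.1% for rho 0 to 0.7. If the open change score were used at rho 0.3 or 0.4, its variance would be 29% or 15% above the unadjusted imputed model.

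**The case against.** The plan's default is valid and deliberate. Section 17.1.3 justifies model (1) by keeping assumptions to a minimum, randomization protects against bias, and section 17.1.5 acknowledges the precision trade-off and states a criterion. The 0.5 is an example, the low-clustering case is unstated, and every saving above depends on one mechanical reading. Section 17.1.3 already promises baseline control in the longitudinal analysis. An unadjusted model also does not depend on T0 scores completed after the visit, which the study procedures in section 6.1 allow. All of this stands, and it makes the point an improvement to a valid plan.

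Three stronger readings are tempting, and the documents do not support them:

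- **Invalid inference.** A reader might infer that a data-driven covariate choice biases the estimate or inflates type I error. Applied mechanically, it does neither. Reporting the best of the unadjusted, covariate-adjusted and change-score results would give about 9-10%, but the plan does not say that it will do this.
- **A large loss of precision.** Against never adjusting, complete-case standard errors fall by about 19% at rho 0.6 and 28% at rho 0.7. At those values the rule nearly always includes T0 (87% and 99% of trials), so most of that gain is already secured.
- **No baseline adjustment planned.** Sections 17.1.3 and 17.1.5 both provide for it; what is missing is one consistent commitment.

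**Conclusion.** The point holds as a low-priority improvement. Model (1) omits T0, section 17.1.5 makes its inclusion depend on an undefined ICC observed after follow-up, and the longitudinal wording in sections 17.1.3 and 17.1.5 does not agree. With 63 completers and imputation, always adjusting cuts the variance relative to the rule by about 4-5%, 5-7%, 2-7%, 0-2% and 0% at rho 0.3, 0.4, 0.5, 0.6 and 0.7. The ranges cover an ICC with or without T1, and the 95% interval is at most about 4% narrower. These figures assume rho, normal data, T2 missing completely at random, no clinician effect and model (1) as the fallback. A separate complete-case run with an assumed clinician ICC of 0.05 and a T0-T2 rule gave standard-error reductions of 3%, 6%, 5%, 2% and 0%. That is slightly larger, as expected without imputation. No feasibility or acceptability endpoint is affected.

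**What to change.** Include T0 PAM-SF as a fixed covariate in model (1) and in the longitudinal model, whatever the ICC, and align the wording of sections 17.1.3 and 17.1.5. Do the same for other linear-model outcomes with a T0 value collected before allocation, such as PSQ-18 and Global PROMIS. Do not extend it to PHQ-8, GAD-7 or the post-visit IPC, which are administered after the visit. Drop the ICC rule, label unadjusted and change-score results as sensitivity analyses, and report the observed T0-T2 correlation for planning the future trial.

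Because pre-visit surveys may be completed after the visit, flag those T0 values and check in a sensitivity analysis that the result does not depend on them.

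The cost is a change of SAP wording, one degree of freedom, and a record of whether each T0 survey was completed before or after the visit. No further data are needed from patients.
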